3.4.3 Data collection

Baseline characteristics of patients randomized to each framing method will be abstracted from the electronic health record and Penn Data Store, and will include age, sex, race/ethnicity, and medical comorbidities. Whether contacted patients created an account on the Way to Health website and/or ultimately consented for enrollment in the study will be captured.

3.4.4 Outcomes

For all outcomes, we will compare patients initially presented with study participation via opt-in framing versus opt-out framing. The primary outcome will be the proportion of patients that enroll in the study. Exploratory outcomes, among patients that ultimately enrolled in the study, will include the proportion of enrolled patients that failed to complete the study, change in daily step count from baseline to the end of the GAME PAD intervention and the end of follow-up (overall and stratified by overall GAME PAD study arm – gamification intervention versus attention control), and change in patient-reported symptom scores from baseline to the end of the GAME PAD intervention and the end of follow-up (overall and stratified by overall GAME PAD study arm)

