**Opt-in versus opt-out clinical trial enrollment
among patients with peripheral artery disease:
A GAME PAD substudy**

Version 2

November 09, 2020

1. Background

Research studies are hampered by low participation rates, threatening these studies' external validity, prolonging study timelines, and increasing costs.(1,2) Behavioral economics research has shown that framing retirement savings and organ donation participation as opt-out rather than opt-in increases participation in these programs while maintaining informed choice.(3) In healthcare, an opt-out approach has also been shown to increase influenza vaccination and human immunodeficiency virus screening.(4,5) More recently, a randomized controlled trial testing opt-in versus opt-out approaches to colorectal cancer screening by fecal occult blood testing showed that the opt-out approach increased participation rates nearly 3-fold.(6)

In clinical trials of home-based monitoring for patients with myocardial infarction and a behavioral intervention for patients with poorly-controlled diabetes mellitus, sub-studies have shown that an opt-out approach increased enrollment compared with an opt-in approach.(7,8) In a trial of a home-based monitoring program for patients with myocardial infarction, eligible patients were enrolled using a traditional opt-in approach.(7) These patients were sent a recruitment letter after their myocardial infarction, contacted via phone and consented for enrollment, and, after consent, sent a remote monitoring medication bottles, entered into a system configured with financial incentives, reminders, and social support. A separate cohort of patients, made ineligible for participation by their insurance type, was sent configured medication bottles along with their recruitment letters to create an opt-out frame. In the opt-in arm, 16% of patients agreed to participate in the study, compared with 38% in the opt-out arm. In a trial of a behavioral intervention for patients with poorly controlled diabetes mellitus, patients were randomized to receive a letter informing them that they had been enrolled in a clinical trial (opt-out) versus a standard recruitment letter (opt-in).(8) In the opt-in arm, 13% of patients agreed to participate compared with 38% in the opt-out arm.

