Though opt-out trial participation has increased enrollment in two prior studies, it is uncertain whether it will do the same in a clinical trial intended to promote physical activity in patients with peripheral artery disease (PAD), as these patients differ from those included in the myocardial infarction and diabetes trial in several ways, and the intervention differs as well. We therefore seek to conduct a randomized substudy of the proposed GAME PAD randomized controlled trial, evaluating the effect of opt-out versus opt-in framing of clinical trial enrollment.

2. Study Objectives

The objectives of this study are the following:

1. To determine the effect of an opt-out versus an opt-in approach to enrollment in a clinical trial enrolling patients with peripheral artery disease on the proportion of patients contacted enrolled
2. To determine the effect of an opt-out versus an opt-in approach to enrollment in a clinical trial enrolling patients with peripheral artery disease on the clinical characteristics of patients who decide to enroll in the study

3. Sub-Study Design and Procedures

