3.1 General overview

The GAME PAD study is a two-arm randomized controlled trial aimed at evaluating whether a home-based walking program with automated coaching augmented with gamification and behavioral economic principles improves functional capacity in patients with PAD. The study will randomize 100 patients with PAD to a 16-week home-based walking program using goal-setting alone (attention control) or to the same home-based walking program with automated coaching augmented with gamification and behavioral economic principles. The study will be conducted using the Way to Health platform, and patients will enroll and consent for participation online, with available help from a study coordinator by telephone. This sub-study will test whether opt-in or opt-out framing of study participation upon initial contact affects the proportion of patients who ultimately enroll in the study and the demographic characteristics of enrolled patients.

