3.4.2 Study arms

Patients randomized to opt-in framing will be instructed to visit the Way to Health website to enroll in the study, or to call or email the study coordinator with questions or for assistance in enrolling. Patients randomized to opt-out framing will receive an email that frames participation in the study as part of the standard of care, and will be informed that a study coordinator will be calling them in the coming days to start enrollment in the study unless they opt out of participation.

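### Does the lack of a time window for enrollment leave the primary comparison to an unstated cut-off?

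*Combined protocol and SAP*

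**What the plan says.** Section 3.4.4 defines the endpoint: "The primary outcome will be the proportion of patients that enroll in the study". Section 2 gives the denominator, since the first objective is the effect of framing "on the proportion of patients contacted enrolled". Section 3.4.3 describes what is recorded: "Whether contacted patients created an account on the Way to Health website and/or ultimately consented for enrollment in the study will be captured". Section 4 compares the arms by chi-square under intention-to-treat, with patients grouped by the framing they first received.

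Two other passages bear on timing. Under section 3.4.2, opt-in patients "will be instructed to visit the Way to Health website to enroll in the study", while opt-out patients are told that "a study coordinator will be calling them in the coming days to start enrollment in the study" unless they decline. Section 3.1 gives the only number that could limit enrollment: "The study will randomize 100 patients with PAD to a 16-week home-based walking program".

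The document does not state a window from email to outcome, a last date for ascertainment, the number of patients to be emailed, or how they are batched. It also does not say whether consent closes at 100.

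**The concern.** A proportion that enroll has a definite value only once it is settled when a patient counts as not enrolled. Here the routes differ: an opt-in patient can act when the email arrives, whereas an opt-out patient may be waiting for a call. If time to consent differs by arm and many contacts are pending when counting ends, both rates are too low, and the slower arm's rate is proportionally lower. Intention-to-treat fixes the arm a patient belongs to, not the length of follow-up. Even with equal delays, where the ratio is preserved, the absolute difference shrinks. A cut-off chosen after the arm rates were seen could move the result either way. This is the only primary outcome, and section 5.6.2 offers the result as a guide to future recruitment, so the size of the effect matters as well as its sign.

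**Working it through.** The plan gives no sample size, power or expected effect for the substudy, so there is no figure to reproduce. The check asks how far the missing window could move the result. Only the rates, the 3:1 ratio (read as opt-in to opt-out) and the target of 100 come from the documents; everything about timing is assumed.

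**1. Complete follow-up.** Section 1 reports for the diabetes trial: "In the opt-in arm, 13% of patients agreed to participate compared with 38% in the opt-out arm". The ratio is 0.38/0.13 = 2.92 and the difference 25 points. The pooled rate at 3:1 is 0.75 × 0.13 + 0.25 × 0.38 = 0.1925, so 100 enrollees need about 100/0.1925 = 519 contacts.

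**2. A cut-off a fixed number of days after the email, no cap.** With exponential delays, observed rate = p × (1 − exp(−days/mean delay)). Assumed mean delays are 3 and 14 days, in either order.

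| Cut-off | Opt-out slower | Opt-in slower |
|---|---|---|
| 14 days | 0.240/0.129 = 1.87 | 0.376/0.082 = 4.58 |
| 30 days | 0.335/0.130 = 2.58 | 0.380/0.115 = 3.31 |
| 60 days | 0.375/0.130 = 2.88 | 0.380/0.128 = 2.96 |

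By 60 days a 14-day mean delay leaves exp(−60/14) = 1.4% of eventual consents uncounted. Only the short cut-offs distort, and no section suggests one.

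**3. A hard stop at the 100th consent.** This was simulated with 2,000 runs per scenario, mailings every 14 days, 3:1 within each mailing and the same delays. For false rejection both arms were given 19.25%.

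| Mailing size | Ratio, unequal delays | False rejection, unequal delays |
|---|---|---|
| 24 | 2.80 to 3.03 | 5–6% |
| 52 | 2.70 to 3.15 | 7–8% |
| 172 | 2.26 to 3.74 | 21–28% |

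A second, independent set of runs agreed within simulation error. With equal delays false rejection was 4.5% to 5.4% at all three sizes. With equal 7-day delays the ratio held, and the difference fell from 25 points to 23.8 (mailings of 52) or 20.5 (mailings of 172).

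**4. Effect on the conclusion.** At 13% and 38%, the chi-square test rejected in at least 99% of runs in every hard-stop scenario.

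**5. A cruder bound without a delay model.** Let f be the share of contacts pending at closure and g the share of their eventual consents already made. The observed rate is p × (1 − f + f × g). With f = 10%, even if every pending opt-in consent and no pending opt-out consent has been made, the rates are 13.0% and 0.38 × 0.90 = 34.2%, a difference of 21.2 points. The same extreme at f = 50% gives 13.0% and 19.0%, with power of about 49%. That would require half of all contacts to be pending at closure with no opt-out consent yet made among them.

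**6. What the wording implies.** Sections 3.1, 3.4.3 and 3.4.4 all use the word *ultimately* for enrollment or consent. Section 2 sets the denominator as those contacted, and section 4 keeps patients in the arm of first contact. Together these describe final status for every emailed patient, with anyone who has not consented counted as not enrolled. Account creation is recorded too, but it is a step before enrollment and not the endpoint.

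**The case for a change.** The strongest argument for a change is that *ultimately* has no date attached, and a trial seeking 100 patients may not stay open to late consenters. Final status then means status at closure, and contacts pending at that moment are counted as failures. The plan does not rule out a few large mailings, and in that case false rejection could exceed 20%. A sentence fixing the window would cost little.

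Part of this stands. The window and the handling of pending contacts are not written down, and with large mailings, abrupt closure and unequal delays the estimated ratio could be well off. A long gap before analysis would not cure that, because the door would already be closed.

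The rest is weaker. Section 3.1 says how many patients the parent trial will randomize, not that consent stops at the 100th. Section 3.3 refers to a separate GAME PAD protocol, which is not available here and may hold the closure rule. A call promised within days sits poorly with a 14-day mean delay in the opt-out arm, and the documents do not show which arm is slower. Concurrent randomization gives both arms the same calendar closure, so the ratio is distorted only if delays differ.

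Operational remedies also have a price. Ending emails at 90 consents and letting everyone finish 60 days would, with mailings of 52, leave the parent trial with 91 to 103 patients (10th to 90th percentile). With mailings of 172 the average would be 109 to 114. Departing from the parent trial's target to protect a substudy endpoint is a debatable trade.

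**Conclusion.** No change to the plan follows. What is missing is a detail of definition that analysts would fill sensibly from the text: final consent status for every emailed patient, by assigned framing, with non-consenters kept in the denominator. Done that way, and with contacts given time to resolve, the comparison is sound; under the assumed delays the ratio at 60 days is 2.88 to 2.96 against 2.92. With small rolling mailings, even a hard stop at 100 moves it only to between 2.80 and 3.03. Serious distortion needs either a cut-off of a few weeks or an abrupt stop combined with a few large mailings and delays differing nearly five-fold.

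This conclusion rests on the Background rates applying here, on exponential delays with means of 3 to 14 days, and on contacts not being left pending in large numbers at closure. The documents can neither confirm nor refute these. If a large share were pending at closure, the size of the effect would need cautious reading.

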3.4.5 Informed consent

Because the trial tests different methods of approaching patients prior to enrollment, informed consent cannot feasibly be obtained and we will request a waiver of informed consent

4. Statistical Analysis

We will compare the primary outcome and attrition rate between patients initially presented with study participation via opt-in framing versus opt-out framing using the chi-square method. Change in step count from baseline through the intervention period and follow-up will be compared using paired t tests, as will change in patient reported symptom scores from baseline through the intervention period and the end of follow up. The primary outcome will be analyzed using the intention-to-treat principle, grouping patients by framing of study participation at initial contact. Other outcomes, among patients that ultimately enrolled in the GAME PAD study, will similarly group patients by framing of study participation at initial contact.

5. Human Research Protection

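### The exploratory step-count and symptom comparisons by framing leave out GAME PAD arm and give no direct framing-by-arm contrast; one linear model would supply both at almost no cost

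*Combined protocol and SAP*

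**What the plan says.** Section 3.1 describes the parent trial: "The study will randomize 100 patients with PAD to a 16-week home-based walking program", with goal-setting alone or with gamification added. Every enrollee in the substudy therefore also belongs to a randomized GAME PAD arm.

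Section 3.4.4 defines the outcomes at issue as exploratory and restricts them to enrollees: "Exploratory outcomes, among patients that ultimately enrolled in the study, will include" change in daily step count and change in symptom scores. Step change is to be compared by framing "overall and stratified by overall GAME PAD study arm – gamification intervention versus attention control". Symptom change is likewise to be compared "overall and stratified by overall GAME PAD study arm".

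Section 4 gives the method: "Change in step count from baseline through the intervention period and follow-up will be compared using paired t tests", and the same for symptom scores. On grouping it says: "Other outcomes, among patients that ultimately enrolled in the GAME PAD study, will similarly group patients by framing of study participation at initial contact". It names no regression model, covariate, arm term or interaction. The document gives no alpha, power, SD or effect size for these outcomes.

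**The concern.** Change in steps is a measure that the gamification program could be expected to move, and each framing group will be a mixture of gamification and control patients. An overall framing comparison without arm leaves any gamification effect in the residual variance, and it does not correct for a chance excess of gamification patients in one framing group.

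The stratified comparison has a different weakness. It yields two framing results, one per arm, with no planned comparison between them. With about 50 patients per arm, one result may be significant and the other not. Readers commonly take that pattern as evidence that the framing difference depends on the intervention, although it arises easily when the difference is the same in both arms. What is at stake is the interpretation of exploratory results.

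**Working it through.** The plan states no figure for these outcomes, so there is none to reproduce. The calculation below is illustrative.

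**Inputs from the document.** 100 enrollees (Section 3.1). Framing allocation 3:1, read as opt-in to opt-out from the order of the sentence (Section 3.4.1). Enrollment rates of 13% or 16% opt-in and 38% opt-out in the two earlier studies (Section 1).

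**Assumptions.** GAME PAD arms 1:1; within-arm SD of change equal to 1; two-sided alpha 0.05; normal approximation; complete outcome data; standardized arm effect d varied.

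**1. Framing split among enrollees.**
- 13% vs 38%: 0.75 × 0.13 = 0.0975 against 0.25 × 0.38 = 0.095, or about 51:49.
- 16% vs 38%: 0.75 × 0.16 = 0.12 against 0.095, or about 56:44.
- No framing effect on enrollment: 75:25.

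**2. Precision lost by omitting arm.** Variance inflation is 1 + d²/4.

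| Assumed d | Variance inflation | SE inflation | Power for a 0.5 SD framing difference, 51:49 |
|---|---|---|---|
| 0 | none | none | 70.5% |
| 0.25 | 1.6% | 0.8% | 69.9% |
| 0.5 | 6.3% | 3.1% | 67.9% |
| 0.8 | 16% | 7.7% | 64.1% |

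With arm in the model, power is 70.5% in every row.

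**3. Chance imbalance in arm.** With 50 of 100 on gamification, the between-framing difference in the proportion on gamification has SD = √[0.25 × (100/99) × (1/n_in + 1/n_out)].
- 51:49: 0.1005. 56:44: 0.1012. 75:25: 0.116.
- At d = 0.5, a one-SD imbalance moves the framing difference by 0.10 × 0.5 = 0.05 SD, against an SE of √(1/51 + 1/49) = 0.20 SD.
- An imbalance of 20 points or more has probability 0.045 (51:49) or 0.069 (56:44). At exactly 20 points the shift is 0.20 × 0.5 = 0.10 SD.

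**4. Two separate within-arm tests.** The SE within one arm is √(2/n_in + 2/n_out), or 0.283 SD at 51:49. Suppose the true framing difference is identical in both arms. The arms contain different patients, so P(exactly one significant) = 2p(1 − p), where p is the within-arm power.
- Difference 0.3 SD: p = 0.185, so 2 × 0.185 × 0.815 = 0.30.
- Difference 0.5 SD: p = 0.424, so 2 × 0.424 × 0.576 = 0.49.
- At 56:44 the results are 0.30 and 0.49. At 75:25, p is 0.151 and 0.334, giving 0.26 and 0.45.

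**5. What an interaction estimate could show.** SE = √2 × within-arm SE.
- 51:49: √2 × 0.283 = 0.40 SD. 75:25: √2 × 0.327 = 0.46 SD.
- Interaction detectable with 80% power: 2.80 × 0.40 = 1.12 SD and 2.80 × 0.462 = 1.29 SD.
- Power for a 0.5 SD interaction: about 24% and 19%.

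**The case against.** The strongest case against the point is that little is lost. Arm is assigned at enrollment, after the framing email, so chance imbalance is ordinary sampling variation that an unadjusted two-sample test already carries in its standard error; the false-positive rate stays near 5%. Noise and imbalance are the same phenomenon seen twice, not two separate harms. The gamification effect size is assumed. The parent trial has its own protocol, which Section 3.3 mentions, and randomization there may be balanced on framing. The stratified comparison already removes arm differences, and an interaction test on 100 patients has little power. All of this stands, and it keeps the point small.

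It does not remove the point. Arm is known for every enrollee and costs one degree of freedom. Low power is a reason to report an interval rather than two p-values, because the interval displays the uncertainty that a split verdict conceals.

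Three stronger readings are tempting and are not supported:
- **That pooling biases the framing comparison.** It does not, because arm is randomized after framing.
- **That effect modification cannot be judged at all.** The planned arm-specific results would allow a difference and its interval to be derived, if estimates and standard errors are reported. What is missing is a commitment to that contrast.
- **That the stratification is meant to test whether response to gamification differs by framing.** The document states no purpose for it. The two objectives in Section 2 concern enrollment and the characteristics of enrollees.

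A more basic fault lies in the same sentence of Section 4. A paired t test assesses change within patients and does not compare two independent framing groups. The figures above assume a between-group comparison, which the plan still has to name.

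**Conclusion.** The point holds as a low-cost improvement to exploratory analyses. Sections 3.4.4 and 4 include neither GAME PAD arm in the overall comparisons nor a direct framing-by-arm contrast. Omitting arm costs modest precision: about 6% in variance at an assumed 0.5 SD arm effect, and nothing if there is no effect. It also leaves uncorrected a chance imbalance with SD about 0.10 in the proportion on gamification.

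The more useful half concerns the within-arm tests. A split result would occur with probability about 0.30 to 0.49 under an identical framing difference of 0.3 to 0.5 SD, or 0.26 to 0.45 if enrollees split 75:25. These figures rest on 1:1 arms, 100 enrollees with complete data, the projected framing splits and the assumed effect sizes. The primary outcome, the proportion enrolled, is not touched.

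**What to change.** In Section 4, replace the paired t tests for step and symptom change with a between-group linear model of change that includes framing and GAME PAD arm; the framing coefficient is the overall comparison. Add one further model with the framing-by-arm term, and report that interaction as an estimate with its 95% CI, labelled exploratory. Present the within-arm framing differences descriptively with intervals, without separate significance claims.

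The cost is two or three sentences of text, one degree of freedom for arm and one more in the interaction model. No new data or operational change is needed. The interaction interval will be wide, roughly ±1.96 × 0.40 = ±0.78 SD at a 51:49 split and ±1.96 × 0.46 = ±0.90 SD at 75:25, and the text should say so in advance.

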3.4.5 Informed consent

Because the trial tests different methods of approaching patients prior to enrollment, informed consent cannot feasibly be obtained and we will request a waiver of informed consent

4. Statistical Analysis

We will compare the primary outcome and attrition rate between patients initially presented with study participation via opt-in framing versus opt-out framing using the chi-square method. Change in step count from baseline through the intervention period and follow-up will be compared using paired t tests, as will change in patient reported symptom scores from baseline through the intervention period and the end of follow up. The primary outcome will be analyzed using the intention-to-treat principle, grouping patients by framing of study participation at initial contact. Other outcomes, among patients that ultimately enrolled in the GAME PAD study, will similarly group patients by framing of study participation at initial contact.

5. Human Research Protection

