3.4. Substudy procedures

3.4.1 Randomization

Eligible patients will be contacted via email to determine their interest in participation in the GAME PAD study. Patients will be randomized 3:1 to an email message framing trial participation in a standard opt-in manner versus an email message framing trial participation in an opt-out manner.

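### Section 4 plans a valid but unadjusted chi-square for the primary outcome, names no effect measure or interval, and leaves unused the baseline covariates collected in both arms; the precision available from them is modest.

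*Combined protocol and SAP*

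**What the plan says.** Objective 1 in Section 2 reads "To determine the effect of an opt-out versus an opt-in approach to enrollment", and the quantity of interest is the proportion of contacted patients who enrol. Section 3.4.4 matches this: "The primary outcome will be the proportion of patients that enroll in the study".

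Section 4 gives one method for that outcome, a comparison of patients "initially presented with study participation via opt-in framing versus opt-out framing using the chi-square method". It fixes the analysis set: "The primary outcome will be analyzed using the intention-to-treat principle, grouping patients by framing of study participation at initial contact". It names no risk difference, risk ratio, odds ratio or confidence interval for the primary outcome, and no covariates.

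On the data available, Section 3.4.3 says: "Baseline characteristics of patients randomized to each framing method will be abstracted from the electronic health record and Penn Data Store". These "will include age, sex, race/ethnicity, and medical comorbidities". The covariates are therefore planned for people who do not enrol as well as for those who do. Section 3.4.1 sets the allocation ("Patients will be randomized 3:1 to an email message framing trial participation in a standard opt-in manner", against the opt-out message) and names no stratification factor.

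**The concern.** A chi-square test says whether two proportions differ. It does not say by how much or with what precision, and that is what Objective 1 asks. The crude difference can be read off the two proportions, but the effect scale and its interval are left open. The substudy states no sample size or precision target, so the interval is what would show a reader how informative the result is.

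The second part concerns efficiency. Age and comorbidity burden plausibly predict who enrols in a walking trial run through a website. In a randomized comparison, adjusting for prognostic baseline covariates and then averaging back to the whole sample estimates the same difference in proportions with a somewhat narrower interval. The covariates are already to be abstracted in both arms, so the primary comparison gives up some precision that would be cheap to recover. The question is how much.

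**Working it through.** The plan gives no sample size, power, alpha or target effect for the substudy, so there is no figure of its own to reproduce. The following sizes the gain under stated assumptions.

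**Inputs**

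- Outcome: binary, analysed by assigned framing (Sections 3.4.4 and 4).
- Allocation: 3:1 (Section 3.4.1), read from the word order as three opt-in to one opt-out, so arm fractions are 0.75 and 0.25.
- Enrolment rates: 13% versus 38% and 16% versus 38%, from the two earlier studies in Section 1. These are background, not design inputs. Lower pairs of 5% versus 10% and 2% versus 4% are my assumptions.
- Number contacted: not stated. The main trial randomizes 100 (Section 3.1). I assume emailing continues until 100 enrol, all through this substudy.
- Prognostic strength: not stated. I assume one normally distributed score in a logistic model, with log-odds slopes per SD of 0.36, 0.55 and 0.75. These give c of about 0.60, 0.65 and 0.70.

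**Step 1: crude interval at 13% versus 38%**

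Contacts: 100 / (0.75 × 0.13 + 0.25 × 0.38) = 100 / 0.1925, about 519, or 390 opt-in and 130 opt-out.

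95% CI half-width: 1.96 × √(0.13 × 0.87/390 + 0.38 × 0.62/130) = 0.090, so the 25-point difference carries about ±9.0 points.

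**Step 2: variance with and without adjustment**

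Let p0 and p1 be the opt-in and opt-out rates, and q0 and q1 a patient's enrolment probabilities given the covariates. The large-sample variances, per patient contacted, are:

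- Unadjusted: p0(1−p0)/0.75 + p1(1−p1)/0.25
- Adjusted (efficient): E[q0(1−q0)]/0.75 + E[q1(1−q1)]/0.25 + Var(q1−q0)

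At 13% versus 38%, the unadjusted value is 0.1131/0.75 + 0.2356/0.25 = 1.093. At c about 0.65, the adjusted value is 0.1092/0.75 + 0.2207/0.25 + 0.0039 = 1.032. The ratio is 0.944, a 5.6% reduction. Interval width scales with √0.944 = 0.972, so it is 2.8% narrower.

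**Step 3: variance reduction over the range**

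| Rates | Contacts for 100 enrolments | Crude half-width | c ≈ 0.60 | c ≈ 0.65 | c ≈ 0.70 |
|---|---|---|---|---|---|
| 13% vs 38% | 519 | 9.0 points | 2.5% | 5.6% | 9.5% |
| 16% vs 38% | 465 | 9.6 points | 2.6% | 5.7% | 9.7% |
| 5% vs 10% | 1,600 | 3.2 points | about 1% | 2.5% | 4.7% |
| 2% vs 4% | 4,000 | 1.3 points | 0.5% | 1.1% | 2.2% |

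In the first row the ±9.0 points becomes about ±8.9, ±8.7 and ±8.6. For c of 0.65 and 0.70 that equals 519 × (1/0.944 − 1) = 31 and 519 × (1/0.905 − 1) = 54 further contacts. In the last row the half-width changes by at most about 0.015 points.

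**Step 4: effect on the test**

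I assume two-sided alpha 0.05. At 13% versus 38% with 519 contacts, unadjusted power already exceeds 99.9%. At 16% versus 38% with 465, a 10% variance reduction moves power from 99.7% to 99.8%. At 2% versus 4% with 4,000, a 2% reduction moves it from 90.6% to 91.1%.

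These are large-sample figures that take the prognostic model as correct. They do not charge for estimating several coefficients from about 100 enrolments.

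**The case against.** The strongest reply is that adjustment is optional here. An unadjusted chi-square is valid under randomization, and no stratification factor calls for a model. The primary outcome is already a proportion per arm analysed by intention to treat, so the crude difference estimates the effect without bias and its interval needs no regression. A model adds decisions: which comorbidities, how to code race/ethnicity, and what to do with missing record values. The covariates also have another role, since Objective 2 concerns the characteristics of those who enrol.

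All of that stands. A reader might infer that the chi-square is wrong, that adjustment is needed to obtain a risk difference, or that substantial precision is being thrown away. The documents support none of these. The third fails on size: even in the favourable case the interval tightens by less than half a point around a 25-point difference.

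The favourable case may also be optimistic. The reported contrast in the myocardial infarction study ("In the opt-in arm, 16% of patients agreed to participate in the study, compared with 38% in the opt-out arm") came from a letter followed by a telephone call in the opt-in arm. Here opt-in patients are emailed and directed to a website (Section 3.4.2). Section 3.3 sets no substudy exclusions while the main trial has its own criteria, so some contacted patients may be unable to enrol. Both features point towards lower rates, where the gain shrinks.

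What the reply does not remove is that the plan states neither an effect measure nor an interval, and that the extra precision, though small, comes from data already being collected and leaves the estimand unchanged when the result is standardized.

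**Conclusion.** The point holds as a low-cost improvement, not as an error in the test. Section 4 should name its effect measure and interval; that part needs no assumption about prognostic strength. By itself it is a missing detail, because the crude difference follows from the two proportions.

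Using the covariates adds a modest gain. With c between about 0.60 and 0.70, variance falls by roughly 2.5% to 10% at rates like 13% versus 38%, and by roughly 0.5% to 2% near 2% versus 4%. The prognostic strength, the enrolment rates and the number contacted are all assumptions outside the plan. The benefit is a slightly narrower interval. At the cited rates it is not expected to alter whether the test is significant.

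**What to change.** In Section 4, state that the primary estimate is the difference in enrolment proportions, opt-out minus opt-in, with the risk ratio, each with a 95% CI. Obtain both by standardization (g-computation) from a logistic model of enrolment on assigned arm plus age, sex, race/ethnicity and a short comorbidity list fixed in advance, with robust or delta-method standard errors. Report the crude risk difference with its 95% CI and the chi-square test beside it. Do not substitute the model's odds ratio for the standardized difference, since that would change the question from the one in Objective 1.

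The cost is about one paragraph of plan wording and slightly more programming, with no new data. The covariate list, its coding and the rule for missing health-record values must be written down before the outcome data are analysed. The list should stay short because only about 100 enrolments can be expected if the main trial's size limits recruitment.
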